We hypothesize that providing information on GA and recommendations to oncology physicians can improve patient-reported outcomes such as HRQoL, which is similar to an approach showing that an early palliative care intervention improved outcomes of patients with advanced lung cancer.⁶⁰ Interventions guided by GA have positive effects on health outcomes including prevention of disability and reduction in the risk of falls, unplanned hospitalizations, and nursing home admissions.^{3,61-63} Several studies have shown that the implementation of GA-driven recommendations into the clinical care of older patients with cancer is feasible.^{4,7} The ELCAPA study illustrated that providing GA information to oncology teams can influence treatment decisions, although outcomes from these interventions were not measured in this study.⁵ Another pilot study showed that GA affected the oncology treatment plan.⁵³ In a study by McCorkle et al.,⁶⁴ geriatric nurse practitioners conducted GA with cancer patients, which led to a survival advantage (67% in the intervention group compared with 40% in the control group) and improved HRQoL. In a study by Goodwin et al., breast cancer patients in the GA-driven recommendations group were significantly more likely to return to normal functioning than controls.⁶⁵ Different approaches for chemotherapy selection and dosing for older and/or frail patients are supported by the literature and are incorporated into the framework as GA-driven recommendations. For example, the FOCUS-2 trial found that chemotherapy for advanced colorectal cancer was safe and efficacious in the older and/or frail patient if started at a 20% dose reduction with escalation as tolerated.⁶⁶ The GA and recommendations utilized in this proposal have been developed through preliminary work, extensive review of the evidence, and clinical expertise of the geriatric oncology physicians on the research team.

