4.2. Entry Criteria for Patients

4.2.1. Inclusion Criteria for Patients

4.2.1a. Male or female 70 years of age or older

4.2.1b. Diagnosis of an advanced solid tumor malignancy (advanced cancer) or lymphoma. In most situations, this would be a stage IV cancer. A patient with a diagnosis of stage III cancer or lymphoma is eligible if cure is not possible or anticipated. Clinical staging without pathological confirmation of advanced disease is allowed.

Must be considering or currently receiving any kind of cancer treatment (any line), including but not limited to hormonal treatment, chemotherapy, monoclonal antibody therapy, or targeted therapy. Patients who are considering therapy are eligible even if they ultimately choose not to be on therapy. Patients with a history of any previous cancer treatment, including radiation and/or surgery are eligible. A patient may also be enrolled on a treatment trial and participate in this study, if all other inclusion and exclusion criteria are met.

4.2.1c. Have at least one geriatric assessment domain meet the cut-off score for impairment other than polypharmacy per Table 2.

4.2.1d. Have visits planned with the oncology physician for at least 3 months and be willing to come in for study visits.

4.2.1e. Able to provide informed consent or, if the oncology physician determines the patient to not have decision-making capacity, a patient-designated health care proxy (per institutional policies) must sign consent by the baseline visit.

4.2.1f. Subject has adequate understanding of the English language because not all GA measures have been validated in other languages.

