Due to the coding schema involving a conditional coding structure, inter rater reliability involved percent agreement in 3 coding areas: number of geriatric concerns, the category of geriatric domain discussed, and the physician's response quality. *A GA communication composite score will be created by adding all GA-related topics that were discussed for each visit.* For number of geriatric concerns, the percent agreement was calculated using the difference in numbers between each coder and the consensus. An average of all coder agreement was calculated for the category of geriatric domain and physician response quality. If inter-rater agreement percentages fell below 70%, the coding team would meet for additional training. The principal investigator remained involved in the coding process and provided guidance or adjudication when necessary.

Another secondary outcome measure will be patient-reported HRQoL as measured by the FACT and caregiver HRQoL (burden) as measured by the Caregiver Reactions Assessment (CRA). We hypothesize that the mean HRQoL for patients and caregivers at sites randomized to the intervention arm will be higher than for those in the usual care arm at 4-6 weeks following the intervention and that this increase will be both statistically significant and clinically meaningful.^{99,100} We will include GA impairment (at baseline and follow up) to evaluate if these influence patient-reported and caregiver-reported HRQoL differently in the intervention versus the control group. Other secondary outcomes will include whether the intervention impacts how the oncology physician acknowledges and addresses age-related concerns, caregiver burden (as measured by the Caregiver Reaction Survey) and caregiver satisfaction with communication (as measured by the modified HCCQ) at 4-6 weeks. We will follow participants for survival for 12 months after enrollment. We will obtain the date, location of death, and cause of death. If a site becomes aware that a study participant is deceased, they should complete the form which is available on the URCC NCORP website. Otherwise sites will be contacted approximately 1 year after each participant was enrolled to assess survival and asked to complete this form.

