11.3.2. Intervention Procedures (Only for sites randomized to the intervention arm)

11.3.2. a. AT THE BASELINE VISIT:

- After the patients have been registered for the study, enter the GA scores into the mycarg.org website or if no internet is available, contact the URCC NCORP Research Base to assist.
- After entering the GA scores, print the built pdf packet specific to that patient.
- Present GA summary form and recommendation forms to oncology physician to review just prior to baseline patient-oncology physician visit. Study staff can assist the oncology physician in the completion of the forms. Study and clinical staff can assist in implementing GA-driven recommendations after physician approves them.
 - Information on cognitive impairment or depression is included in the summary.
 - The oncology physician MUST review and sign the summary form and recommendations forms.
 - GA recommendations that are planned by the oncology physician for the patient should be check-marked by the end of the visit.
- Three copies of the GA summary and GA recommendations forms should be made: one should be provided to the patient, one should be provided to the caregiver (if requested), and one should be retained in the study chart.
- The original forms should be sent into the URCC Research Base.

11.3.3. Oncology Physician Assessment for Patients: After the audio-recorded baseline visit, oncology physicians will complete a brief survey (on paper) to capture factors that influenced the decision-making process for the patient's plan.

11.3.4. Submitting Materials to the URCC Research Base:

11.3.4a. After the audio-recorded baseline visit, site study staff should ensure the forms below are completed and submit them to the URCC Research Base:

- All oncology physician, patient and caregiver assessments from above
- All CRA Study Forms
- Audio-recordings (submitted and stored as per training) with Audio-recording Data Form
- Intervention summary and recommendation forms (if applicable).

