15.4. Other Secondary Analyses

15.4.1. Secondary Aim 2: HRQoL will be assessed with the FACT and Caregiver HRQoL will be assessed with the Caregiver Reactions Assessment (CRA). The analysis will be the same as that used for Primary Aim 1. We will include geriatric assessment impairment (at baseline and follow up) to evaluate if these influence patient-reported HRQoL differently in the intervention versus the control group. We will also compare whether the uptake of geriatric assessment recommendations influences patient reported HRQoL and caregiver burden. Data from the intervention arm will be fit to a linear mixed model with FACT or CRA as the outcome, number and percent of implemented interventions (number implemented/number recommended) as the fixed effect, and NCORP site as a random effect independent of residual error. Analyses will be adjusted for treatment status.

15.4.2. Secondary Aim 3: We will compare the effect of the intervention on caregiver satisfaction (the modified health care climate questionnaire for the caregiver) using the same linear mixed model methodology.

15.4.3. Exploratory Aims: Exploratory aims will evaluate (1) whether the number of discussions about age-related issues during the clinic visit correlates with patient satisfaction, (2) whether the intervention increases the proportion of age-related concerns that are acknowledged and addressed, and (3) if communication about age-related issues influences how patients, caregivers, and oncology physicians make decisions for cancer treatment. An additional exploratory aim will examine the impact of the intervention on survival.

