- 1.2. *Geriatric assessment*: Assessment tools comprising the comprehensive geriatric assessment are discussed below. The various assessment tools were selected based upon extensive data in the geriatric literature demonstrating predictive value as well as feasibility data in multiple studies of elderly patients with cancer. Other than the cognitive and physical performance measures, the assessments are self-administered. Patients who cannot complete the assessment on their own can receive assistance from the study personnel or caregiver. The comprehensive assessment is performed first prior to treatment and brief follow-up GA measures are collected at 4-6 weeks, 3 months, and 6 months. Measures collected only at baseline are noted with ***.
 - 1.2.1. *Activities of daily living (ADL)*:¹ ADLs are measures of self-care. ADL independence will be assessed using the Katz Index of Independence in Activities of Daily Living, commonly referred to as the Katz ADL. The Katz ADL is the most appropriate instrument to assess functional status as a measurement of the patient's ability to perform activities of daily living independently. Clinicians typically use the tool to detect problems in performing activities of daily living and to plan care accordingly. The Index ranks adequacy of performance in the six functions

of *bathing, dressing, toileting, transferring, continence, and feeding*. Patients are scored yes/no for independence in each of the six functions. A score of 6 indicates full function, 4 indicates moderate impairment, and 2 or less indicates severe functional impairment.

1.2.2. *Instrumental Activities of Daily Living (IADL)*:² Self-reported functional status will be assessed using the IADL subscale of the Multidimensional Functional Assessment Questionnaire: Older American Resources and Services (OARS). The IADL subscale consists of seven questions rated on a three-point Likert scale. It measures the degree to which an activity can be performed independently.

1.2.3. *Fall History*: A self-reported history of falls in the past six months will be recorded. A history of a recent fall has been demonstrated to be independently predictive of increased risk for chemotherapy toxicity in older cancer patients.³

1.2.4. *OARS Physical Health*:² Self-reported questions that assess the degree of difficulty with physical tasks such as walking, climbing stairs, stooping, and reaching. This measure correlates with disability and comorbidity.

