2.3. Geriatric Assessment

2.3.1. *Timed Up and Go*³⁰: The Timed Up & Go is a performance based test of functional status, measuring how many seconds it takes to stand up from a standard arm-chair, walk 3 meters (10 feet), turn, walk back to the chair, and sit down again. In community dwelling older adults, there was inter-rater and intra-rater reliability (intra-class correlation coefficient 0.99 for both).

2.3.2. *Mini-Cog*: A tool that is validated in the geriatric population to quickly assess cognitive impairment.^{31,32} The Mini-Cog takes approximately 3 minutes to administer. It has minimal language content, which reduces cultural and educational bias. It combines a 3-item recall component with a Clock Drawing Test.

2.3.3. *Short Blessed Orientation-Memory-Concentration (BOMC) Test*³³: A six-question evaluation that screens for cognitive impairment. Studies have shown its validity as a screening instrument and the correlation of its results with those of more extensive mental status tests.

2.3.4. *Nutritional Status and Mini Nutrition Assessment (MNA)*: Screening for nutritional deficit will be performed with body mass index (BMI) evaluation and self-reported weight loss. Further nutritional evaluation will be performed with *the Mini-Nutritional*

*Assessment*** (MNA)³⁴*, a well validated screening measure for nutritional deficiency which has shown to be prognostic of survival in older patients with cancer. Weight will be assessed at each time point. Height will be measured at baseline.

- 2.3.5. *Short Physical Performance Battery:³⁵* Physical performance measures objectively evaluate mobility and fall risk. Falls are common in older cancer patients and predictive of adverse outcomes.
- 2.3.6. *Labs:* CRA will send results of baseline tests collected including hemoglobin, liver function tests, and renal function.
- 2.3.7. *Polypharmacy* will be ascertained from the medical record after patients have been asked to review their medication list on file for any changes in the *Polypharmacy Log and Polypharmacy High Risk Drug Review*.

3. Caregiver Packet

- 3.1. *Demographics***:* Age, race and ethnicity, gender, highest level of education achieved, employment status, marital status, and presence of a living companion will be captured. Additionally, we will collect information on underlying health conditions (*Physical Health*).

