### 4.4 Other Secondary Analyses

#### 4.4.1. Secondary Aim 2

HRQoL will be assessed with the FACT-G and Caregiver HRQoL (burden) will be assessed with the Caregiver Reactions Assessment (CRA). We will include geriatric assessment impairment (at baseline and follow up) to evaluate if these influence patient-reported HRQoL differently in the intervention versus the control group. We will also compare whether the uptake of geriatric assessment recommendations influences patient reported HRQoL and caregiver burden. Data from the intervention arm will be fit to a linear mixed model with the FACT-G or CRA as the outcome, number and percent (number implemented/number recommended) of interventions as the fixed effect, and NCORP site as a random effect independent of residual error. Analyses will be adjusted for treatment status.

#### 4.4.2. Secondary Aim 3

We will compare the effect of the intervention on caregiver satisfaction (the modified health care climate questionnaire-age for the caregiver) using the same linear mixed model methodology.

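### Secondary Aim 2 treats follow-up GA impairment, measured after the intervention, as an effect modifier for HRQoL; only baseline impairment can serve that purpose

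*SAP*

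**What the plan says.** SAP 4.4.1 names FACT-G and the Caregiver Reactions Assessment (CRA) as the Secondary Aim 2 measures and then says "We will include geriatric assessment impairment (at baseline and follow up) to evaluate if these influence patient-reported HRQoL differently" in the intervention and control groups. Protocol 15.4.1 has the same sentence. Protocol 7.2 extends it to caregivers: "We will include GA impairment (at baseline and follow up) to evaluate if these influence patient-reported and caregiver-reported HRQoL differently". SAP 4.4.1 and Protocol 15.4.1 also call for adjustment for treatment status.

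For the main HRQoL comparison, Protocol 15.4.1 says "The analysis will be the same as that used for Primary Aim 1": a linear mixed model with arm as fixed effect and practice site as random effect. SAP 4.1 gives that model for outcomes in general, but SAP 4.4.1 does not repeat the cross-reference.

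On timing, Protocol 11.3.2 has the GA summary and recommendations delivered at the baseline visit, and "Study and clinical staff can assist in implementing GA-driven recommendations after physician approves them". Appendix X-1 says "brief follow-up GA measures are collected at 4-6 weeks, 3 months, and 6 months". Neither document plans an analysis with a follow-up GA score as the response.

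**The concern.** An effect modifier has to be fixed before the intervention can act on it. Baseline GA impairment meets that condition. Follow-up impairment may not. Recommendations are generated from the patient's own GA scores (Protocol 10 and 11.3.2), and the pilot summaries listed interventions where a score showed impairment (Protocol 1.8.4). The rationale in Protocol 1.7 says "Interventions guided by GA have positive effects on health outcomes including prevention of disability and reduction in the risk of falls".

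If the intervention works on impairment, some Arm 1 patients leave the impaired group because of it. Those who remain are not comparable with impaired patients in Arm 2. A benefit confined to patients impaired at baseline would then be understated, and a reader could draw the wrong conclusion about who gains from GA feedback.

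There is also a measurement problem. The plan does not say how domains are combined into impairment, and the follow-up GA is shorter than the baseline GA, so the same word covers two different quantities.

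**Working it through.** **1. Which domains can be rescored at follow-up.** Table 2 of the protocol set against the schedules in Appendix X-1 (Tables 1 and 3):

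| Table 2 domain | Baseline tools | Repeated at follow-up |
|---|---|---|
| Physical function | ADL, IADL, falls, OARS Physical Health | all four |
| Physical performance | SPPB, Timed Up and Go | SPPB |
| Psychological | GAD-7, GDS | GDS |
| Cognition | BOMC, Mini-Cog | Mini-Cog |
| Nutrition | BMI, MNA, weight loss | no form scheduled, but "Weight will be assessed at each time point" (Appendix X-1, 2.3.4) |
| Comorbidity | OARS Comorbidity | none |
| Social support | OARS Medical Social Support | none |
| Polypharmacy | medications, laboratory | none |

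Baseline: 4+2+2+2+3+1+1+2 = 17 tools in 8 domains. Follow-up: 4+1+1+1 = 7 tools in 4 domains, or 5 domains if nutrition is derived from weight. The single Social Activities item is repeated but has no Table 2 cut-off. An any/none coding would also be constant at baseline, because eligibility requires "Have at least one geriatric assessment domain meet the cut-off score for impairment other than polypharmacy per Table 2".

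**2. Effect on the contrast that the sentence asks about.** The documents give no inputs for this, so all of the following are assumptions.

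- Baseline score M0 ~ N(0,1); impaired if M0 > c, with prevalence p.
- Follow-up score M1 = rho·M0 + sqrt(1 - rho²)·e - d·(Arm 1 and impaired at baseline), with d = 0.5 SD.
- HRQoL Y = -b·M1 + sqrt(1 - b²)·e2, with b = 0.4, 0.5 or 0.6.
- rho = 0.5 or 0.7.
- p = 26% (the pilot clinic's positive depression screens, Protocol 1.8.4), or p = 64%, the midpoint of that clinic's 68% functional impairment and 60% poor physical performance.

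The true arm effect on Y is b·d in patients impaired at baseline and 0 in the rest. The true difference between groups is therefore 0.5·b = 0.20, 0.25 or 0.30 SD.

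Grouped by follow-up status, the arm effect is b times the amount by which mean M1 is lower in Arm 1 within that group. Numerical integration over M0 gives:

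| p | rho | M1 lower by, impaired at follow-up | M1 lower by, not impaired | Difference | Times b = 0.4 / 0.5 / 0.6 |
|---|---|---|---|---|---|
| 26% | 0.5 | 0.082 | 0.027 | 0.055 | 0.022 / 0.028 / 0.033 |
| 26% | 0.7 | 0.122 | -0.003 | 0.126 | 0.050 / 0.063 / 0.075 |
| 64% | 0.5 | 0.183 | 0.047 | 0.136 | 0.055 / 0.068 / 0.082 |
| 64% | 0.7 | 0.214 | 0.004 | 0.210 | 0.084 / 0.105 / 0.126 |

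So 0.20-0.30 SD becomes about 0.02-0.08 SD at 26% prevalence and about 0.05-0.13 SD at 64%. Two things produce the shrinkage: follow-up status is an imperfect stand-in for baseline status, and Arm 1 patients who improve move out of the impaired group. With d = 0 both groupings give zero, so there is no bias.

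**3. Precision, for scale.** Detectable arm difference (80% power) = 2.8·sqrt((4/n)·(1 + (n/68 - 1)·ICC)), using the 68 sites in the SAP, with n and ICC assumed.

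- n = 500, ICC 0.01: 2.8·sqrt(0.008 × 1.0635) = 0.26 SD.
- n = 330, ICC 0.05: 2.8·sqrt(0.01212 × 1.193) = 0.34 SD.

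For a difference between impairment groups at p = 26%, multiply by 1/sqrt(0.26 × 0.74) = 2.28, which gives about 0.59-0.77 SD.

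**The case against.** The strongest reply is that this is a subsidiary sentence under one secondary aim, and that the HRQoL comparison that matters is specified without the term. That stands. A reader might infer from SAP 4.4.1 alone that the impairment analysis is the only arm comparison on HRQoL, and so that the Secondary Aim 2 result is itself biased. Protocol 15.4.1 and SAP 4.1 do not support that: both give the arm model without GA terms. What remains is that SAP 4.4.1 does not say whether the GA terms enter the main model or a separate one.

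A reader might also infer that the analysis would show harm where there is none. Suppose impairment falls by 0.2 SD in all Arm 1 patients and HRQoL does not change. An arm main effect adjusted for the follow-up score would then be -0.08 to -0.12 SD. But the plan asks whether impairment acts differently by arm, not for that adjusted main effect. In the same scenario the arm-by-impairment difference is 0.00 with the continuous score and within about 0.04 SD of zero with a yes/no grouping.

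Third, no stated aim names improvement in GA impairment, and Protocol 1.7 describes other studies. Usual-care physicians are also told of GDS or BOMC scores of 11 or more at baseline, and GDS is notified in both arms at follow-up, which narrows any contrast. This stands as far as it goes: that the intervention changes impairment is plausible on the protocol's own reasoning, not stated as a goal.

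Fourth, the inputs are assumed and the interaction is poorly powered either way. A fall in impairment of 0.1-0.2 SD with b = 0.5 would give a true difference of only 0.05-0.10 SD. That is fair. It also means the analysis will be read from its estimate and interval, and the estimate is what shifts.

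Fifth, a brief follow-up GA is openly described, and Table 2 gives a cut-off for every repeated tool. So the shorter battery is not an error, and impairment is not wholly undefined; only the way of combining domains is missing. Nor can the sentence be read as mediation, since no mediation method or assumption is given.

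**Conclusion.** The point holds for the follow-up half of the effect-modification analysis in SAP 4.4.1, Protocol 15.4.1 and Protocol 7.2. Follow-up impairment is measured after an intervention that may change it, and it can be scored on at most five of eight domains. It is therefore not a valid effect modifier.

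If the intervention lowers impairment by 0.5 SD only in patients impaired at baseline, and benefits HRQoL through that route, a true difference of 0.20-0.30 SD appears as about 0.02-0.13 SD. The result depends on prevalence (26% or 64%) and on the baseline to follow-up correlation (0.5 or 0.7), none of which the documents supply for this trial. If impairment does not change, nothing is biased.

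The baseline half of the analysis is sound. The main FACT-G and CRA arm comparison is sound provided follow-up impairment is kept out of it. The primary aim and Secondary Aims 1 and 3 are not touched. The change is worth making because it costs almost nothing and removes a possible bias, not because a main conclusion of the trial is at risk.

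**What to change.** In SAP 4.4.1, Protocol 15.4.1 and Protocol 7.2, replace the sentence with text to this effect:

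> Effect modification will be assessed with baseline GA impairment only, for example the number of Table 2 domains impaired at baseline. For FACT-G and for the Caregiver Reactions Assessment, the mixed model will contain arm, baseline impairment and their interaction, with practice site as a random effect and the planned adjustment for treatment status. The interaction will be reported with a 95% confidence interval. The relation of follow-up GA scores to HRQoL will be reported as an association, or in a separately declared mediation analysis, and not as effect modification.

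Add to SAP 4.4.1 that the main arm comparison of FACT-G and the CRA is the Primary Aim model and does not include follow-up impairment.

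This keeps the caregiver analysis of Protocol 7.2 and the treatment-status adjustment, and needs no new data. The cost is that the plan can no longer claim that a patient's current impairment modifies the effect of the intervention.

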inadequate social support; 20% had an abnormal cognition screen (but had decision making capacity);⁷⁴ 34% had recently fallen, and 60% had poor physical performance.^{23,75} Acceptability of summaries: We have developed and revised the GA summaries based on extensive qualitative and written feedback from the patients and their caregivers. The summaries include a description of the test used to assess the domain in lay language, an interpretation of the score for each domain, and a list of interventions to consider if the score signifies impairment. Acceptability of GA-driven recommendations: On average, 80% of the GA-driven recommendations were implemented by the referring oncology physician with an average of 6 interventions per patient (range 3-15).

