## 4 Statistical Analysis

### 4.1 Statistical Considerations

This is a cluster-randomized trial with NCORP practice sites being the clusters. Because of the cluster randomized study design, we will apply linear mixed model methodology. The outcome will be the response, and the arm will be the fixed effect. NCORP practice sites will be entered as a random effect independent of residual error. Estimation will be performed using Restricted Maximum Likelihood, and the null hypothesis of zero mean difference between arms will be tested using a F test. The specific NCORP practice site differences will be assessed graphically using Best Linear Unbiased Predictors (BLUP) of the mean response for each NCORP.

All regression analyses will include terms to control for study site and oncologist type. In addition, clinically important socioeconomic variables such as patient gender, age, race/ ethnicity, and cancer variables such as cancer type and treatment status will be used to control for patient-level covariates. In case a key covariate is found to be unbalanced between study arms, it will be included in the model as a potential confounder.

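### The one-arm uptake model omits baseline impairment, so it could show that implementing more recommendations lowers quality of life when there is no effect

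*SAP*

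**What the plan says.** Under Secondary Aim 2, SAP 4.4.1 sets out an uptake analysis: "Data from the intervention arm will be fit to a linear mixed model with the FACT-G or CRA as the outcome", with "number and percent (number implemented/number recommended) of interventions as the fixed effect" and site as a random effect. It then says "Analyses will be adjusted for treatment status". Protocol 15.4.1 has the same model, with "number and percent of implemented interventions (number implemented/number recommended) as the fixed effect". Neither document says whether number and percent go into one model or two.

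Three other statements bear on which covariates this model contains:

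- The same SAP paragraph brings in GA impairment at baseline and follow-up, "to evaluate if these influence patient-reported HRQoL differently in the intervention versus the control group".
- SAP 4.1 applies to all regressions. It adds site, oncologist type, and "clinically important socioeconomic variables such as patient gender, age, race/ ethnicity, and cancer variables such as cancer type and treatment status".
- SAP 4.1 also has an imbalance rule: "In case a key covariate is found to be unbalanced between study arms, it will be included in the model as a potential confounder".

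**The concern.** The analysis is confined to one arm, so randomisation does not protect it. The exposure is also not independent of how ill the patient is. Protocol 11.3.2 has site staff enter the GA scores into a website that builds a packet for that patient, and Protocol 1.8.4 describes summaries that list interventions where a score indicates impairment. A patient with more impaired domains therefore receives more recommendations and can have more of them implemented. SAP 2.3 itself says that the issues measured by GA can affect quality of life. Impairment thus sits behind both the exposure and the outcome, which is confounding by indication.

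At stake is a misleading secondary result. A trial that tests GA-driven recommendations could report that following more of them goes with worse quality of life, when the coefficient only reflects who was more impaired at the start. The same reasoning applies to the Caregiver Reaction Assessment if caregivers of more impaired patients report more burden.

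**Working it through.** The documents give no effect size or power for this analysis, so there is no figure of its own to reproduce. As a check on the arm size used below: 31/0.95 = 32.6, rounded up to 33, and 16 x 33 = 528, the accrual target. One arm is 8 x 31 = 248 evaluable patients.

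**Inputs from the documents.** There are eight GA domains (SAP Appendix B), with at least one impaired by eligibility. In the pilot, 80% of recommendations were implemented, "with an average of 6 interventions per patient (range 3-15"). There are 8 sites per arm with 31 subjects each and alpha 0.05, taken as two-sided (2.5% per direction). The alternative layout splits the 68 sites as 34 per arm with 7 patients each (238), which is an assumption.

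**Assumptions.** Impaired domains D run from 1 to 8 with mean 3.9. The number recommended R rises with D, with mean 6.1; this reads the pilot's 6 as recommended rather than implemented. The number implemented K is Binomial(R, 0.8). The site ICC is 0.1. The correlation of D with quality of life runs from 0 to -0.4. The true effect of implementation is exactly zero. The SAP 4.1 covariates and treatment status were not simulated.

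**Direction, by formula.** With D omitted, the expected coefficient on K is (effect of D on the outcome) x Cov(K, D)/Var(K). As a worked case, take D uniform on 1 to 8, R Poisson(1.5D) and 80% implemented, so that K given D is Poisson(1.2D):

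- E(D) = 4.5 and Var(D) = 63/12 = 5.25
- Cov(K, D) = 1.2 x 5.25 = 6.30
- Var(K) = 1.2 x 4.5 + 1.44 x 5.25 = 5.40 + 7.56 = 12.96
- Ratio = 6.30/12.96 = 0.486

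If each impaired domain costs 1, 2 or 3 FACT points (assumed), the false coefficient is -0.49, -0.97 or -1.46 points per implemented recommendation. Simulation of this case gave -0.47, -0.95 and -1.43. A bell-shaped distribution of D gave -0.27, -0.52 and -0.78. The sign is stable, but the size depends on the spread of impairment.

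**Error rates.** Random-intercept model for site, REML, 600 trials per setting, 8 x 31 patients:

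| Correlation of D with quality of life | Number alone: mean coefficient (SD of FACT-G) | Number alone: false harm | Joint model: number, false harm | Joint model: percent, false benefit | Number alone plus D: false harm |
|---|---|---|---|---|---|
| 0 | no bias | 2.3% | 2.0% | 3.0% | not needed |
| -0.1 | -0.038 | 17.8% | 24.2% | 10.8% | 2.5% |
| -0.2 | -0.073 | 50.7% | 66.5% | 24.8% | 3.7% |
| -0.3 | -0.111 | 84.7% | 97.2% | 56.2% | 2.7% |
| -0.4 | -0.149 | 98.5% | 100% | 79.7% | 2.8% |

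The mean coefficient is about 0.37 times the correlation in each row (for example 0.111/0.3 = 0.37), as the formula implies. With 600 trials, a true 2.5% has a 95% simulation range of 2.5% +/- 1.96 x sqrt(0.025 x 0.975/600), or about 1.25% to 3.75%. The last column lies inside that range.

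The 34 x 7 layout gives nearly the same false harm for number alone: 3.5%, 16.7%, 48.3%, 82.2% and 98.0%. The larger number of sites does not cure the problem.

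**Percent.** Entered alone, percent is close to nominal (2.2% to 3.0% false harm) if the uptake rate is unrelated to impairment. At correlation -0.3 in the 34 x 7 layout, it gives 37.0% false harm if uptake rises 5 points per impaired domain, and 39.8% false benefit if uptake falls 5 points. In the joint model its bias is toward benefit because, at a given number implemented, a higher percent means fewer recommendations and hence less impairment.

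**Number recommended as the adjuster instead of D.** This works when uptake is unrelated to impairment. When uptake varies by 5 points per domain (correlation -0.3, 34 x 7), it leaves 11.0% false benefit or 14.2% false harm, depending on the direction.

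**The case against.** The strongest reply is that the plan already adjusts for a good deal. A reader who sees only SAP 4.4.1 might infer that the model holds nothing but uptake, site and treatment status. SAP 4.1 does not support that, because it adds oncologist type, demographics and cancer type to every regression, and its list is open-ended. Age and cancer type may carry some information on impairment, so the error rates above could be somewhat lower in practice. But neither impairment nor baseline quality of life is named.

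The sentence on GA impairment in the same SAP paragraph is the next best defence. Its stated purpose is to see whether impairment acts differently in the two arms. The uptake model comes afterwards, with its own terms and no control group. The imbalance rule does not help either, since a one-arm model has no between-arm imbalance to trigger it.

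Three further inferences go beyond the documents:

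- *That the analysis will report harm.* The correlation between impairment and quality of life is not given, and at zero there is no bias.
- *That percent will show a false benefit.* This needs joint entry with number, or uptake that falls as impairment rises. The wording on joint entry is open, and the documents say nothing about how uptake varies with impairment.
- *That pilot counts describe this trial.* The pilot came from a referral geriatric clinic with mean age 82.1, so the counts may not transfer.

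It can also be said that this is a minor, non-randomised analysis. That is true and limits its weight. However, it stands under a secondary aim and asks about influence, while the hypothesis-generating caveat in SAP 4.4.3 is attached to a different analysis.

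**Conclusion.** The concern holds as a possible bias with a firm direction for number implemented. Under no true effect, number alone could show that more implementation goes with lower quality of life, in 17.8% to 98.5% of trials at assumed correlations of -0.1 to -0.4 with 248 patients, against a nominal 2.5%. The size rests on that correlation, on the assumed spread of impaired domains, and on recommendations rising with impairment. Only the last of these is supported by the documents. Percent alone is about unbiased unless uptake varies with impairment, and then it can err either way. Importance is low: no primary or between-arm result depends on this model.

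**What to change.** In SAP 4.4.1 and Protocol 15.4.1:

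1. Add the baseline number of impaired GA domains and the baseline score of the outcome modelled (FACT-G or Caregiver Reaction Assessment) as covariates in the uptake model. Use baseline impairment, not follow-up impairment, which implementation could itself change. Do not use number recommended as a substitute.
2. State that number implemented and percent implemented are fitted in separate models.
3. Label the result a non-randomised, hypothesis-generating association within the intervention arm.

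The cost is a wording change and two covariates. Protocol Appendix X-1 already schedules the GA items and the Caregiver Reaction Assessment at screening and the FACT at baseline. A domain count may leave some residual confounding by severity within domains, which is a further reason for the label in item 3.
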